3. GLOSSARY

PET: Positron Emission Tomography

MR: Magnetic Resonance Imaging

PSA: Prostate specific antigen

RP: radical prostatectomy

EBRT: External beam radiation therapy

4. INTRODUCTION AND RATIONALE

Medical imaging requires innovation to support personalized care. This need is particularly emerging in the setting of prostate cancer (PCa) recurrence, a condition that affects up to 50% of patients treated with radical prostatectomy (RP) or external-beam radiotherapy (EBRT) as primary treatment for clinically localized disease.(1) When biochemical recurrence (BR) is detected, an accurate identification of location and extent of cancer recurrence is mandatory in order to address patients to directed therapies with prolonged intervals of cancer-free survival (e.g. surgical resection and/or radiation treatment on the specific site of recurrence), thus avoiding systemic treatments, including androgen deprivation therapy.(2)

Imaging plays a key role in identifying local or distant recurrence when Prostate-Specific Antigen (PSA) level is rising.(3)

Positron Emission Tomography/Computed Tomography (PET/CT) by using Choline radiolabeled with either ¹¹C or ¹⁸F is the most established imaging modality in PCa restaging; however, its low detection rate for low PSA values hampers the real usefulness of this imaging modality within this specific therapeutic window of opportunity.(4,5) The limitation related to low PSA values might be due both to the integration of CT into PET/CT scanner, which is not the best morphological imaging modality to detect local PCa relapse, and to the low sensitivity of Choline as radiotracer.

The recent introduction of integrated PET/Magnetic Resonance Imaging (MR) paves the way to a completely innovative imaging approach for PCa recurrence, by overcoming several limitations of the currently available imaging modalities. The combined simultaneous acquisition of PET and multiparametric MR (mp-MR) provides metabolic, structural and functional imaging information regarding prostate cancer status in a whole-body single session examination, with better soft tissue contrast and reduced radiation exposure in comparison to PET/CT.(6,7) Although some evidence regarding the clinical value of the individual component of this imaging modality have been reported so far, very few data on the incremental value of combined PET/MR in PCa recurrence are currently available.

Moreover, differently from CT, MR imaging consists of several sequences that can be applied depending on the specific clinical questions that need to be addressed and on the anatomical region that requires to be evaluated. Nowadays, there is still no consensus regarding the optimal acquisition protocols that should be performed to accurately restage PCa.(8)

Along with technological advances, alternative radiotracers have been proposed to overcome the limitations of Choline.

New molecular probes targeting the Prostate-Specific Membrane Antigen (PSMA) have been developed, showing high expression in PCa cells.(9) Among the available tracers and ligands to image PSMA-expressing tumours, Glu-NH-CO-NH-Lys-(Ahx)-[⁶⁸Ga(HBED-CC)] (⁶⁸Ga-PSMA) is currently one of the most successful and promising PSMA radioligands for PCa, improving the detection rate of metastases in patients with biochemical recurrence, even at low serum PSA values.(10) Encouraging results have been also achieved with ⁶⁸Ga-labeled DOTA-4-amino-1-carboxymethyl-piperidine-DPhe-Gln-Trp-Ala-Val-Gly-His-Sta-Leu NH₂ (⁶⁸Ga-Bombesin) radiotracer, a synthetic bombesin receptor antagonist targeting gastrin-releasing peptide receptors (GRPr), which are overexpressed in 63%–100%

of human prostate cancer tissue; this radiotracer has been proposed as a new promising molecular probe for PET imaging in biochemical recurrence of PCa with (11-14) However, very limited data are currently available on its role in this clinical setting.

A well-suited technology such as PET/MR, combining mp-MR together with PET metabolic imaging by using radiotracers alternative to Choline and potentially more specific, represents an innovative powerful diagnostic tool that will surely have a burning impact on the diagnostic workflow of patients with PCa recurrence and therefore on personalized treatment.

5. STUDY OBJECTIVES

5.1 Primary

To provide an innovative approach to restage patients with biochemical recurrence of prostate cancer by using hybrid PET/MR with innovative radiotracers (68Ga-PSMA and 68Ga-Bombesin)

5.2 Primary and secondary specific aims

Primary aim

To evaluate the diagnostic accuracy of 68Ga-PSMA PET/MR to identify the site of recurrence in patients with biochemical relapse of PCa after primary treatment and comparison with the performances of 68Ga-Bombesin PET/MR

Secondary aims

- To correlate 68Ga-PSMA PET/MR and 68Ga-bombesin-PSMA PET/MR imaging with clinical and pathological features.
- To evaluate the results of a lesion-targeted approach in terms of biochemical-recurrence-free survival and clinical recurrence-free survival. A particular effort will be made in order to identify patients that might benefit most from this approach in terms of predictors of both positive imaging findings as well as response to local treatment of metastatic sites with both surgery and radiation therapy.

6. STUDY DESIGN

6.1 Description of the protocol

Prospective monocentric study (Phase II study).

Sixty consecutive patients with biochemical recurrence (PSA \geq 0.2 ng/ml), previously treated with radical prostatectomy for organ confined prostate cancer will be enrolled; patients with previous and/or concomitant androgen deprivation therapy will be excluded from enrolment.

All patients will undergo both 68Ga-PSMA PET/MR and 68Ga-Bombesin PET/MR imaging at San Raffaele Scientific Institute in two different days; all clinical and pathological variables available at the time of PET/MR studies will be recorded for each patient.

PET/MR results will be compared to other imaging procedures performed and available in the course of routinely work-up evaluation. Treatment approach will be based on all available clinical and instrumental data, including 68Ga-PSMA and 68Ga-Bombesin PET/MR, evaluated during multidisciplinary sessions including expert Urologists, Nuclear Medicine and Radiologist physicians. Patients with local recurrence will be candidate to salvage radiation therapy (sRT). Patients presenting only LN recurrence will be proposed to be submitted to salvage lymph node (LN) dissection (sLND) or sRT; alternatively, conventional androgen deprivation therapy will be performed in those patients who will not be willing to undergo secondary surgery or radiation therapy.

To assess the diagnostic accuracy of 68Ga-PSMA and 68Ga-Bombesin PET/MR, images will be validated with: 1) histology (when deemed necessary by the clinician as expected under the normal care pathway) obtained by echographically-guided biopsy in suspected local recurrence or during sLND in the event of suspected nodal recurrence; 2) biochemical response after tailored treatment in patients submitted to sRT for local or LN recurrence 3) conventional imaging modalities performed to assess disease status as part of the routine clinical work-up. 68Ga-PSMA and 68Ga-Bombesin PET/MR will be

correlated with available clinical and pathological features. To assess the impact of 68Ga-PSMA PET/MR and 68Ga-Bombesin PET/MR in changing patients' management, patients will be followed-up after the execution of PET/MR studies. Patients will be followed-up until the end of the study period.

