1. SYNOPSIS

COMPOUNDS:

- Glu-NH-CO-NH-Lys-(Ahx)-[68Ga(HBED-CC)] (68Ga-PSMA)
- Bombesin receptor antagonist (68Ga-Bombesin)

Study number: PCa Restaging – PET/MR

TITLE: Phase II prospective monocentric study on prostate cancer restaging by using PET/MR with innovative radiotracers	
TRIAL LOCATION U.O. Medicina Nucleare, IRCCS Ospedale San Raffaele / PI: Prof.ssa [name]	
STUDY OBJECTIVE(S)	
Overall goal: To provide an innovative approach to restage patients with biochemical recurrence of prostate cancer by using hybrid PET/MR with innovative radiotracers (68Ga-PSMA and 68Ga-Bombesin)
 
Primary endpoint:
 
 - To evaluate the diagnostic accuracy of 68Ga-PSMA PET/MR to identify the site of recurrence in patients with biochemical relapse of PCa after primary treatment and comparison with the performances of 68Ga-Bombesin PET/MR 
Secondary endpoint
 
 - To correlate 68Ga-PSMA PET/MR and 68Ga-bombesin-PSMA PET/MR imaging with clinical and pathological features. - To evaluate the results of a lesion-targeted approach in terms of biochemical-recurrence-free survival and clinical recurrence-free survival. A particular effort will be made in order to identify patients that might benefit most from this approach in terms of predictors of both positive imaging findings as well as response to local treatment of metastatic sites with both surgery and radiation therapy.
STUDY DESIGN	
Prospective monocentric study, 60 total patients enrolled. Phase II, open, uncontrolled study.
 
After exclusion of patients with contraindications to PET/MR examinations (See inclusion/exclusion criteria), the 60 enrolled patients will be submitted to both 68Ga-PSMA PET/MR and 68Ga-bombesin PET/MR imaging at our Institution.
 
Each PET/MR study will have a duration of approximately 2 hours (including approximately 1 hour of waiting time and 1 hour of execution of 68Ga-PSMA or 68Ga-Bombesin PET/MR study). To correlate 68Ga-PSMA PET/MR and 68Ga-bombesin-PSMA PET/MR imaging with clinical and pathological features, the following variables will be tested:
 
 - Age - Pre-operative PSA - Pathological Gleason score - Pathological stage - Time to biochemical recurrence

	
- PSA slope - PSA doubling time
 
Patients with the diagnosis of local recurrence will be submitted to standard clinical work-up procedures.

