
Patients presenting only LN recurrence will be proposed to be submitted to salvage lymph node (LN) dissection (sLND) or sRT; alternatively, conventional androgen deprivation therapy will be performed in those patients who will not be willing to undergo secondary surgery or radiation therapy.
 
To assess the diagnostic accuracy of 68Ga-PSMA and 68Ga-Bombesin PET/MR, images will be validated with: 1) histology (when deemed necessary by the clinician as expected under the normal care pathway) obtained by echographically-guided biopsy in suspected local recurrence or during sLND in the event of suspected nodal recurrence; 2) biochemical response after tailored treatment in patients submitted to sRT for local or LN recurrence 3) conventional imaging modalities performed to assess disease status as part of the routine clinical work-up.
 
The validation procedures reported in point 1), 2) and 3) will be performed according the timing required by the routine clinical work-up of the patient and so they could be performed at any time during the course of the study.
 
68Ga-PSMA and 68Ga-Bombesin PET/MR will be correlated with available clinical and pathological features. To assess the impact of 68Ga-PSMA PET/MR and 68Ga-Bombesin PET/MR in changing patients' management, patients will be followed-up after the execution of PET/MR studies. Patients will be followed-up until the end of the study period.
	

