2. FLOW CHART

	T0	T1	T2*
Inclusion/exclusion criteria evaluation	X		
Informed consent administration	X		
68Ga-PSMA or 68Ga Bombesin PET/MR study		X	
68Ga-PSMA or 68Ga Bombesin PET/MR study			X

* ≥ 48 hours \leq 1 month from T1

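### Impact on management is to be assessed, but intended management is not recorded before the scans and nothing allows a change to be attributed to one tracer

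*Combined protocol and SAP*

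**What the plan says.** Section 6.1 states that the impact of the two PET/MR studies on management will be assessed, and gives the means in the same sentence: "in changing patients' management, patients will be followed-up after the execution of PET/MR studies". The synopsis, under patients treatment and procedures, makes the same statement with the same means: "patients will be followed-up after the execution of PET/MR studies".

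On how treatment is chosen, section 6.1 says: "Treatment approach will be based on all available clinical and instrumental data, including 68Ga-PSMA and 68Ga-Bombesin PET/MR, evaluated during multidisciplinary sessions". On what is collected around the scans, it says: "all clinical and pathological variables available at the time of PET/MR studies will be recorded for each patient". In the synopsis, the list introduced by "the following variables will be tested" holds age, pre-operative PSA, Gleason score, stage, time to recurrence, PSA slope and PSA doubling time.

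The flow chart (section 2) puts eligibility ("Inclusion/exclusion criteria evaluation") and consent at T0. T1 and T2 each hold one scan, in either order ("68Ga-PSMA or 68Ga Bombesin PET/MR study").

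Management change is not among the aims in section 5.2 or the three aims numbered in section 11. Neither the statistical part of the synopsis nor section 12.2 defines or analyses it.

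**The concern.** A change in management compares what was intended before the scans with what was decided after them. Follow-up after the scans supplies only the second half. The study is uncontrolled, so no comparison group can stand in for the first half.

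Two things are at stake. First, a reported change would rest on someone judging, with the results known, what would otherwise have been done. That judgement is open to hindsight and could bias the figure. Second, the sentence names both tracers, and comparing them is part of the primary aim, so a reader of the results will want to know what each one contributed. A treatment decision that draws on both gives no basis for that split.

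The loss cannot be repaired at analysis, because an intention that was not written down before the scans can no longer be recorded prospectively.

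**Working it through.** **1. The plan's own figure.** The sample size (section 12.1) rests on sensitivity for lymph node metastasis and not on management. Inputs: 60 patients, 35% prevalence, 80% sensitivity, 95% confidence.
- Expected node-positive patients: 60 × 0.35 = 21.
- Half-width: 1.96 × √(0.80 × 0.20 / 21) = 17.1 points, inside the stated 18.

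The statement that 60 is sufficient holds on this formula, and the present point does not touch it.

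**2. What a measured change needs, against what the plan provides.**

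| Needed | Provided |
|---|---|
| Intended management before any PET/MR | Not named: T0 is eligibility and consent; recorded items are clinical and pathological variables |
| Management after the scans | Yes: multidisciplinary decision and follow-up |
| Definition of a change | None |
| Analysis of change | None in the synopsis or section 12.2 |
| A way to separate the tracers | None: no decision point between T1 and T2, no rule for tracer order, no staged disclosure |

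One of the five elements is in place.

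**3. What the repair would deliver.** The documents give no change rate, so 30% and 50% are assumptions. The formula is half-width = 1.96 × √(p(1 − p)/n).

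Both scans together, n = 60:
- p = 0.30: 1.96 × √(0.21/60) = 11.6 points.
- p = 0.50: 1.96 × √(0.25/60) = 12.7 points.

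One tracer disclosed first, with the order balanced over 60 patients, n = 30 per order:
- p = 0.30: 1.96 × √(0.21/30) = 16.4 points.
- p = 0.50: 1.96 × √(0.25/30) = 17.9 points.

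Pooling the two orders into a first-disclosed and a second-disclosed tracer would restore n = 60, but the result would belong to neither tracer. Tracer-specific figures have to be reported by order, with the wider intervals.

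**The case against.** The strongest objection is about weight. Management change is neither an aim nor an endpoint. It is one descriptive sentence, written twice, and deleting or qualifying it would remove the problem. That is fair, and it limits the point to an inexpensive improvement. It does not remove the point, because the sentence still commits the study to an assessment that its stated method does not support.

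Four stronger readings are tempting and should not be drawn.
- *Change cannot be measured at all.* The documents do not show this. The flow chart is sparse and also omits follow-up and adverse events, which are described elsewhere, and the CRF itself is not part of the documents. A prior plan might be reconstructed from routine records. What can be said is that no prospective record is planned and that reconstruction is open to hindsight.
- *Both tracers' results are released together.* No section says when results are released, the scans fall on different days up to a month apart, and sessions are mentioned in the plural. Joint disclosure is an inference from the sentence on treatment decisions. The firm statement is that nothing provides for separate disclosure.
- *Reconstruction inflates the impact.* Nothing in the documents fixes the direction of bias.
- *A separate effect was promised for each tracer.* The sentence can equally mean the combined work-up. On that reading attribution was never offered, and the remedy is to say so plainly.

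Staged disclosure is also not free. Reports would have to be held back until the session, including that of a first scan done up to a month earlier, and nuclear medicine physicians and radiologists who sit in the session may have read the scans.

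**Conclusion.** The point holds as a modest one. As written, the plan records what was done after the scans and calls for no record of what was intended before them. A change in management could therefore only be reconstructed with the results known, and no section offers a way to assign it to 68Ga-PSMA or to 68Ga-Bombesin. This rests on the text of the protocol and not on arithmetic.

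A reader might infer that the primary accuracy aim or the sample size is undermined. Neither is: management change enters neither of them.

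If the missing record is added, 60 patients would estimate the effect of both scans together to within 11.6 to 12.7 points. This assumes change rates of 30% to 50% and complete forms in all 60 patients. Tracer-specific estimates would carry about 16.4 to 17.9 points on the same assumed rates, and only under staged disclosure.

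**What to change.** 1. Add a CRF item at T0 recording intended management before any PET/MR, in fixed categories taken from the options section 6.1 already names (salvage radiation therapy, salvage lymph node dissection, androgen deprivation therapy), with a category for anything else.
2. Record the same item after the multidisciplinary decision, and define a change as a difference in category.
3. In section 12.2, state that the proportion changed will be reported with a 95% CI as the effect of both scans together, and that no tracer-specific claim will be made.
4. Only if staged disclosure proves feasible, report results by tracer and by disclosure order, with about 30 patients per order.
5. If the T0 item is not added, limit the sentence in section 6.1 and in the synopsis to describing the treatment given after both scans.

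Steps 1 to 3 cost one short form completed twice per patient and a few lines of protocol text. The treatment decision still uses all available data. Step 4 costs more, since reports must be held back and their release controlled, and it is optional.

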6.2 Duration of study

Total duration of the study: 3 years.

For each patient the time of patient direct involvement will be approximately 2 hours for each PET/MR study (duration: approximately 1h after i.v. administration and approximately 1h for the duration of each PET/MR examination).

The patients will be followed-up up to until the end of the study period.

7. SELECTION OF PATIENTS

7.1 Number of patients planned

- 60 prostate cancer adult patients: the enrolled patients will undergo to 68Ga-PSMA PET/MR and 68Ga-Bombesin PET/MR 68Ga-PSMA PET/CT.

7.2 Inclusion criteria

1. Patients with histological proven diagnosis of prostate cancer.
2. Patients treated with radical therapy (RP or EBRT, with or without further adjuvant therapies), who present rising serum PSA values ≥ 0.2 ng/mL.
3. Age ≥ 18 years-old.
4. Willing to provide a signed informed consent.

7.3 Exclusion criteria

1. Age < 18 years-old.
2. previous and/or concomitant androgen deprivation therapy will be excluded.
3. Any additional medical condition that may significantly interfere with study compliance.
4. Contraindications to MR study (i.e. Pacemaker)
5. Known hypersensitivity to

8. TREATMENTS

In addition to the execution of 68Ga-PSMA PET/MR and 68Ga-Bombesin PET/MR scans, all the other imaging procedures and treatment strategies performed will be in the course of routine work-up patient management.

68Ga-PSMA PET/MR and 68Ga-Bombesin PET/MR study:

Tracers synthesis will be performed in our Department following IMPD. 68Ga-PSMA PET/MR study will start 60 minutes after the administration of 160 ± 50 MBq of 68Ga-PSMA and 68Ga-Bombesin study will start 45 minutes after the administration of 140 ± 50 MBq of 68Ga-Bombesin. For both scans the following protocol will be applied:

- localizer MR scans to define the number of table positions (PET-FOV) to acquire (4-min/table position); specific attenuation correction and anatomical localization MR sequences at each PETFOV; pelvic multi-parametric MR protocol according to European Society of Urogenital Radiology (ESUR) guidelines.
Gadolinium-based paramagnetic contrast agent will be injected intravenously with a dose of 0.1mmol/kg and an injection rate of 4 ml/sec. The MR protocol may be modified according to specific clinical requirements.

- PET-acquisition will start from the mid-thigh to the base of the skull base to exploit the reduced ⁶⁸Ga-PSMA and ⁶⁸Ga-Bombesin ligand uptake in the urinary system after pre-scan voiding. Acquisition should proceed from the lower end of the axial field of view cranially in order to minimize misalignment for the urinary bladder which tends to fill up during the time of the examination. PET scans will be acquired in three-dimensional (3D) mode with an acquisition time of usually 2–4 min per bed position. Overall, PET coverage will be identical to the anatomical MR scan range.

8.1 Investigational Medicinal Product (IMP)

⁶⁸Ga-PSMA dossier: see attached file (IMP dossier).

⁶⁸Ga-Bombesin dossier: see attached file (IMP dossier).

8.2 Responsibilities

The investigator or other personnel allowed to dispense Investigational Products is responsible for ensuring that the IMP used in the clinical trial is securely maintained as specified and in accordance with the applicable regulatory requirements. The Investigational Products are to be used as directed by this clinical trial protocol.

8.3 IMP accountability and compliance

All IMP shall be dispensed in accordance with the Investigator's prescription and it is the Investigator's responsibility to ensure that an accurate record of IMP issued is maintained.

9. STUDY PROCEDURES

9.1 Efficacy

Positive PET/MR findings will be compared to :

- 1) histology (when deemed necessary by the clinician as expected under the normal care pathway) obtained by echographically-guided biopsy in suspected local recurrence in the prostate lobe or during pelvic and/or extraperitoneal lymph node dissection in the event of suspected nodal recurrence
- 2) Clinical and laboratory data of the same patients (i.e. serum PSA assay) foreseen within the normal clinical work-up.
- 3) Conventional imaging modalities performed to assess disease status as part of the routine clinical work-up including CT, pelvic mp-MR, MR and bone scintigraphy.
- 4) A comparison between the two modalities will be also performed.

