
STUDY POPULATION
 
Main selection criteria: Prostate cancer patients who experienced biochemical recurrence after primary treatment.
 
Total expected number of patients: 60
	
Inclusion criteria:
 
 1. Patients with histological proven diagnosis of prostate cancer. 2. Patients treated with radical therapy (RP or EBRT, with or without further adjuvant therapies), who present rising serum PSA values ≥ 0.2 ng/mL. 3. Age ≥ 18 years-old. 4. Willing to provide a signed informed consent. 
Exclusion criteria
 
 1. Age < 18 years-old. 2. Previous and/or concomitant androgen deprivation therapy will be excluded. 3. Any additional medical condition that may significantly interfere with study compliance. 4. Contraindications to MR study (i.e. Pacemaker)

INVESTIGATIONAL PRODUCT(S)
 
Formulation(s):
 
 1. Glu-NH-CO-NH-Lys-(Ahx)-[^{68}Ga(HBED-CC)] (^{68}Ga-PSMA) 
Route(s) of administration: intravenously
 
Dose regimen: 160 ± 50 MBq
 
 2. Bombesin receptor antagonist (^{68}Ga-Bombesin) 
Route(s) of administration: intravenously
 
Dose regimen: 140 ± 50 MBq
	

EFFICACY CRITERIA: ^{68}Ga-PSMA PET/MR and ^{68}Ga-Bombesin PET/MR findings will be assessed as follow :
 
 1) histology (when deemed necessary by the clinician as expected under the normal care pathway) obtained by echographically-guided biopsy in suspected local recurrence in the prostate lobe or during pelvic and/or extraperitoneal lymph node dissection in the event of suspected nodal recurrence 2) Clinical and laboratory data of the same patients (i.e. serum PSA assay) foreseen within the normal clinical work-up. 3) Conventional imaging modalities performed to assess disease status as part of the routine clinical work-up including CT, pelvic mp-MR, MR and bone scintigraphy. 4) A comparison between the two modalities will be also performed. 	

SAFETY CRITERIA: data concerning safety and the registration of adverse events will be collected.
	

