
STUDY PROCEDURES
 
Sixty consecutive patients with biochemical recurrence ($\text{PSA} \geq 0.2$ ng/ml), previously treated with radical prostatectomy for organ confined prostate cancer will be enrolled during the whole duration of the study (36 months). Patients with previous and/or concomitant androgen deprivation therapy will be excluded from enrolment.
 
All patients will undergo both ^{68}Ga-PSMA PET/MR and ^{68}Ga-Bombesin PET/MR imaging at San Raffaele Scientific Institute in two different days (> 48 hours between the two studies) and within one month one from the other; all clinical and pathological variables available at the time of PET/MR studies will be recorded for each patient. PET/MR results will be compared to other imaging procedures performed and available in the course of routinely work-up evaluation.
	

PATIENTS TREATMENT AND PROCEDURES
 
Treatment approach will be based on all available clinical and instrumental data, including ^{68}Ga-PSMA and ^{68}Ga-Bombesin PET/MR, evaluated during multidisciplinary sessions including expert Urologists, Nuclear Medicine and Radiologist physicians. Patients with local recurrence will be candidate to salvage radiation therapy (sRT).
	

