
STATISTICAL CONSIDERATIONS
	
The sample size was computed based on sensitivity analysis for PET/MR in predicting lymph node metastasis. Assuming an average prevalence of lymph node metastasis of 35%, a total sample size of 60 patients is sufficient for evaluating a sensitivity of 80% with an absolute precision of 18% (at 95% confident level).
 
8Ga-Bombesin PET/MRI and 68Ga-PSMA PET/MRI will be compared. Sixty patients treated with radical prostatectomy with biochemical recurrence of prostate cancer (PSA < 0.2 ng/ml and raising) will be evaluated and recruited in the study. They will be submitted to both 68Ga-PSMA PET/MR and 68Ga-bombesin PET/MR. Clinical and pathological variables will be recorded for each patient. The exact sites of recurrence as well as the size of all lesions will be recorded for all patients at both imaging procedures. A direct comparison between the two tracers will be performed using Chi-square test for categorical variables.
 
Univariable and multivariable logistic regression analyses will be used in order to identify the predictors of positive imaging at both 68Ga-PSMA PET/MR and 68Ga-bombesin PET/MR.
 
In patients with evidence of local recurrence submitted to salvage radiation therapy the biochemical response to radiotherapy will be used as confirmation of the positivity of imaging.
 
In patients with nodal only recurrence, a salvage pelvic and/or retroperitoneal lymph node dissection according to the site of the positive nodes will be proposed. For patients undergoing nodal dissection, a direct comparison between PET studies and histopathological examination in terms of site and size of the recurrent nodes will be performed. The performance characteristics of both 68Ga-PSMA PET/MR and 68Ga-bombesin PET/MR will be evaluated and compared through accuracy, sensitivity, specificity, positive and negative predictive value in a patient-based as well as in a lesion-based approach.
 
For the evaluation of the response to lesion-targeted treatments Kaplan-Meier analyses as well as univariable and multivariable Cox regression analyses will be performed.

DURATION OF STUDY PERIOD
	
Total duration of the study: 3 years.
 
Each patient will perform two PET/MRI studies in two different days. Each study will last

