	approximately 2 hours (including approximately 1h of waiting time and 1 hour of execution of PET/MRI study). If available, patients will be followed up until the end of the study period.
--	--

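### No rule classifies negative scans or patients without a reference result, and Section 9.1 compares only positive findings, so planned sensitivity and specificity are open to partial-verification bias

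*Combined protocol and SAP*

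**What the plan says.** The primary aim (Section 5.2) is the diagnostic accuracy of 68Ga-PSMA PET/MR for the site of recurrence, compared with 68Ga-Bombesin PET/MR. Section 12.2 plans accuracy, sensitivity, specificity, PPV and NPV, per patient and per lesion.

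On which scans meet a reference, the wording differs:

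- Section 9.1: "Positive PET/MR findings will be compared to" a list of references.
- Synopsis, efficacy criteria, with nearly the same list: "PET/MR findings will be assessed as follow".
- Section 6.1, and the matching Synopsis text: "images will be validated with" histology, biochemical response after salvage radiotherapy, or conventional imaging.

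On how a reference result arises:

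- Histology is at the clinician's discretion and comes from biopsy or dissection where recurrence is suspected.
- Section 12.2 uses the response to radiotherapy to confirm positive imaging, and proposes dissection where nodes are positive.
- Section 6.1: "Treatment approach will be based on all available clinical and instrumental data, including 68Ga-PSMA and 68Ga-Bombesin PET/MR".
- Synopsis, on timing: the validation procedures "will be performed according the timing required by the routine clinical work-up of the patient and so they could be performed at any time" in the study.
- Synopsis, duration: "If available, patients will be followed up until the end of the study period". Sections 6.1 and 6.2 promise follow-up without that condition.

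Section 11 keeps patients who cannot be followed up in the accuracy analysis. It does not say how those with no reference result are classified.

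**The concern.** Sensitivity needs the false negatives and specificity needs the true negatives, so both depend on reference results in scan-negative patients or regions. Here the scans help decide who has biopsy, dissection or radiotherapy, and so who obtains the stronger references. If positives are verified more often than negatives and unverified cases are dropped, sensitivity is inflated and specificity is deflated.

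Routine imaging, PSA and follow-up could verify negatives, but their timing is not fixed. The plan has no definition of a true or false negative, no hierarchy of references, no code for a missing reference, and no correction or sensitivity analysis. All patients enter with rising PSA (Section 7.2), so the entry PSA cannot show that a negative scan is right. The main accuracy figures would then depend on a coding choice made after the data are seen.

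**Working it through.** **The plan's own figure.** Section 12.1 gives 60 patients, 35% nodal prevalence, 80% sensitivity and 18% precision at 95% confidence. Node-positives needed: 1.96² × 0.8 × 0.2 / 0.18² = 18.97, or 19; 18.97 / 0.35 = 54.2 patients. With 60 patients, 0.35 × 60 = 21 node-positives, and the Wald half-width is 1.96 × √(0.16/21) = 17.1 points. Sixty is sufficient as stated.

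**Inputs for the illustration.** From Section 12.1: N = 60, prevalence 35%, sensitivity 80%. Assumed: true specificity (Sp) 80%, 90% or 95%; 80% of positives and 20% of negatives verified (v+ = 0.8, v− = 0.2); verification depends only on the scan result.

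**Unverified cases dropped.**

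- Apparent sensitivity = Se·v+ / [Se·v+ + (1−Se)·v−] = 0.64 / (0.64 + 0.04) = 94%, whatever the specificity or prevalence.
- Apparent specificity = Sp·v− / [Sp·v− + (1−Sp)·v+]. At Sp = 0.9: 0.18 / (0.18 + 0.08) = 69%.
- If v+ = v−, the rates cancel and there is no bias.
- With v− = 0.4 and Sp = 0.9: sensitivity 0.64/0.72 = 89%, specificity 0.36/0.44 = 82%.

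**Unverified negatives counted as true negatives, unverified positives dropped.** At Sp = 0.9 the full table is TP 16.8, FN 4.2, FP 3.9, TN 35.1. Verified: TP 13.44, FN 0.84, FP 3.12, TN 7.02. Unverified negatives: 0.8 × 39.3 = 31.44.

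- Specificity = (7.02 + 31.44) / (38.46 + 3.12) = 92%.
- NPV = 38.46 / (38.46 + 0.84) = 98%; true NPV = 35.1/39.3 = 89%.
- Sensitivity stays at 94%.

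| Assumed true specificity | Specificity, dropped | Specificity, counted as TN | True NPV | NPV, dropped | NPV, counted as TN |
|---|---|---|---|---|---|
| 80% | 50% | 85% | 88% | 88% | 98% |
| 90% | 69% | 92% | 89% | 89% | 98% |
| 95% | 83% | 96% | 90% | 90% | 98% |

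**NPV when verification of negatives depends on disease-related factors** (Sp = 0.9, unverified dropped). With 50% of false negatives and 20% of true negatives verified: 7.02 / (7.02 + 2.10) = 77%. With 20% and 50%: 17.55 / (17.55 + 0.84) = 95%. The true value is 89%.

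**The case against.** The opening word of Section 9.1 is probably a slip. The Synopsis gives almost the same list without it, and specificity and NPV cannot be computed from positives alone. This stands, and it limits a stronger reading: a reader might infer that the plan forces 100% sensitivity and 0% specificity. That needs the literal word, which other sections contradict, plus scoring each tracer only on its own positives, which no section states. A verified site positive on one tracer and negative on the other is a false negative for the second even under Section 9.1. The point therefore rests on how references arise and on the missing rules, not on that word.

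Some negatives may well be verified: PET-negative nodes removed at dissection, cases negative on one tracer only, and patients covered by routine imaging or follow-up. True, but no section says how these count. Accuracy might also be meant only for dissected patients, because the accuracy sentence follows "For patients undergoing nodal dissection, a direct comparison between PET studies and histopathological examination". That reading is possible but not stated, and Section 6.1 lists other references for the same purpose.

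Verification through routine care is a reasonable choice for a single-centre phase II study. It stands as a choice of procedures, but it does not remove the need for a classification rule. The magnitude is indeed not derivable from the documents.

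**Conclusion.** The concern holds. The wording conflict must be reconciled, and the planned sensitivity and specificity are open to partial-verification bias that the plan neither prevents nor corrects. The direction in the dropped-case analysis follows if positives are verified more often than negatives. The size is illustrative: 94% apparent against 80% true sensitivity, and specificity of 50% to 83% or 85% to 96% depending on coding, under assumed verification rates and specificities. The table covers nodal disease only, which is narrower than the primary aim; its non-diseased patients are free of nodal disease, not of recurrence.

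Three further inferences are not supported:

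- That NPV is biased in any event. It is unbiased if unverified negatives are dropped and verification depends only on the scan result. It is at risk if unverified negatives are counted as true, if none are verified, or if verification of negatives depends on other disease-related factors.
- That the 18% precision in Section 12.1 is wrong. It is not.
- That one tracer is favoured. The documents give no basis for unequal verification between tracers.

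**What to change.** 1. **Sections 9.1 and 6.1 and the Synopsis.** Use one wording under which positive and negative reads of both tracers are classified, per patient and per region, against the available reference. State the hierarchy of references, a code for no reference, and what counts as a true negative when every patient has rising PSA.
2. **Section 12.2.** Report detection rate, PPV, and the number verified by scan result and reference type. Report sensitivity, specificity and NPV only where negatives are verified (for example within the dissected template, labelled conditional on surgery), or with a stated verification-bias correction or best/worst-case bounds.
3. **Section 11.** Keep patients with no reference result in the detection-rate and correlation analyses; use them for accuracy only in the bounds.

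The cost is protocol and analysis wording plus a CRF field for reference type by region; no patient or procedure is added. The downside is real. Headline accuracy becomes conditional or bounded, many patients may be coded as having no reference, and no missing result is recovered. Bounds can be wide: in the 80%/20% case with 90% specificity and no prevalence assumption, sensitivity runs from 13.44/45.72 = 29% to 17.58/18.42 = 95%, and specificity from 7.02/14.28 = 49% to 38.46/41.58 = 92%.
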